## **Privacy and Confidentiality**

24. Every precaution must be taken to protect the privacy of research subjects and the confidentiality of their personal information.

## **Informed Consent**

- 25. Participation by individuals capable of giving informed consent as subjects in medical research must be voluntary. Although it may be appropriate to consult family members or community leaders, no individual capable of giving informed consent may be enrolled in a research study unless he or she freely agrees.
- 26. In medical research involving human subjects capable of giving informed consent, each potential subject must be adequately informed of the aims, methods, sources of funding, any possible conflicts of

interest, institutional affiliations of the researcher, the anticipated benefits and potential risks of the study and the discomfort it may entail, post-study provisions and any other relevant aspects of the study. The potential subject must be informed of the right to refuse to participate in the study or to withdraw consent to participate at any time without reprisal. Special attention should be given to the specific information needs of individual potential subjects as well as to the methods used to deliver the information.

After ensuring that the potential subject has understood the information, the physician or another appropriately qualified individual must then seek the potential subject's freely-given informed consent, preferably in writing. If the consent cannot be expressed in writing, the non-written consent must be formally documented and witnessed.

All medical research subjects should be given the option of being informed about the general outcome and results of the study.

- 27. When seeking informed consent for participation in a research study the physician must be particularly cautious if the potential subject is in a dependent relationship with the physician or may consent under duress. In such situations the informed consent must be sought by an appropriately qualified individual who is completely independent of this relationship.
- 28. For a potential research subject who is incapable of giving informed consent, the physician must seek informed consent from the legally authorised representative. These individuals must not be included in a research study that has no likelihood of benefit for them unless it is intended to promote the health of the group represented by the potential subject, the research cannot instead be performed with persons capable of providing informed consent, and the research entails only minimal risk and minimal burden.
- 29. When a potential research subject who is deemed incapable of giving informed consent is able to give assent to decisions about participation in research, the physician must seek that assent in addition to the consent of the legally authorised representative. The potential subject's dissent should be respected.
- 30. Research involving subjects who are physically or mentally incapable of giving consent, for example, unconscious patients, may be done only if the physical or mental condition that prevents giving informed consent is a necessary characteristic of the research group. In such circumstances the physician must seek informed consent from the legally authorised representative. If no such representative is available and if the research cannot be delayed, the study may proceed without informed consent provided that the specific reasons for involving subjects with a condition that renders them unable to give informed consent have been stated in the research protocol and the study has been approved by a research ethics committee. Consent to remain in the research must be obtained as soon as possible from the subject or a legally authorised representative.
- 31. The physician must fully inform the patient which aspects of their care are related to the research. The refusal of a patient to participate in a study or the patient's decision to withdraw from the study must never adversely affect the patient-physician relationship.
- 32. For medical research using identifiable human material or data, such as research on material or data contained in biobanks or similar repositories, physicians must seek informed consent for its collection, storage and/or reuse. There may be exceptional situations where consent would be impossible or impracticable to obtain for such research. In such situations the research may be done only after consideration and approval of a research ethics committee.

## **Use of Placebo**

33. The benefits, risks, burdens and effectiveness of a new intervention must be tested against those of the best proven intervention(s), except in the following circumstances:

Where no proven intervention exists, the use of placebo, or no intervention, is acceptable; or

Where for compelling and scientifically sound methodological reasons the use of any intervention less effective than the best proven one, the use of placebo, or no intervention is necessary to determine the efficacy or safety of an intervention

and the patients who receive any intervention less effective than the best proven one, placebo, or no intervention will not be subject to additional risks of serious or irreversible harm as a result of not receiving the best proven intervention.

Extreme care must be taken to avoid abuse of this option.

#### **Post-Trial Provisions**

34. In advance of a clinical trial, sponsors, researchers and host country governments should make provisions for post-trial access for all participants who still need an intervention identified as beneficial in the trial. This information must also be disclosed to participants during the informed consent process.

#### Research Registration and Publication and Dissemination of Results

- 35. Every research study involving human subjects must be registered in a publicly accessible database before recruitment of the first subject.
- 36. Researchers, authors, sponsors, editors and publishers all have ethical obligations with regard to the publication and dissemination of the results of research. Researchers have a duty to make publicly available the results of their research on human subjects and are accountable for the completeness and accuracy of their reports. All parties should adhere to accepted guidelines for ethical reporting. Negative and inconclusive as well as positive results must be published or otherwise made publicly available. Sources of funding, institutional affiliations and conflicts of interest must be declared in the publication. Reports of research not in accordance with the principles of this Declaration should not be accepted for publication.

## **Unproven Interventions in Clinical Practice**

37. In the treatment of an individual patient, where proven interventions do not exist or other known interventions have been ineffective, the physician, after seeking expert advice, with informed consent from the patient or a legally authorised representative, may use an unproven intervention if in the physician's judgement it offers hope of saving life, re-establishing health or alleviating suffering. This intervention should subsequently be made the object of research, designed to evaluate its safety and efficacy. In all cases, new information must be recorded and, where appropriate, made publicly available.

DEQS	Dry Eye-related Quality-of-Life Score	
FAS	full analysis set	
QD	quaque die	
QoL	quality of life	
IOP	intraocular pressure	
IVRS	Interactive Voice Response System	
IWRS	Interactive Web Response System	
LogMAR	logarithm of the minimum angle of resolution	
MedDRA	Medical Dictionary for Regulatory Activities	
МН	medical history	
OD	oculus dexter (right eye)	
OS	oculus sinister (left eye)	
OU	oculus uterque (both eyes)	
PPS	per-protocol set	
PT	preferred term	
SAE	serious adverse event	
SANDE	Symptom Assessment iN Dry Eye questionnaire	
SAP	statistical analysis plan	

Abbreviation	Explanation
SAS	Statistical Analysis System
SDTM	Study Data Tabulation Model
SOC	system organ classification
TBUT	Tear Breakup Time
TEAE	treatment-emergent adverse event
VA	Visual Acuity

1. INTRODUCTION

This statistical analysis plan (SAP) specifies the statistical methods and analyses to be implemented for the data collected from the IKERVIS PAES study within the scope of Santen's Protocol NVG14L127, "A phase IIIb, prospective, interventional, multicentre, three-year study to explore the long-term evolution of sign and symptoms, and occurrence of complications in dry eye disease subjects with severe keratitis receiving IKERVIS® (1mg/ml ciclosporin) eye drops". It applies to the study protocol Amendment 1 (version 3.0), dated 17-OCT-2018, and provides detailed instructions as to how each analysis will be performed.

Results obtained from the analyses specified in the final approved version of the SAP will become the basis of the clinical study report (CSR) for this protocol. Deviations from the final approved version of the SAP must be substantiated by sound statistical reasoning and documented in the CSR.

REVISION HISTORY FROM THE PREVIOUS VERSION (1.0):

- Reflected the latest version of MedDRA (Sec. 4.4)
- Updated the definitions of ocular surface complication (Sec. 4.4.1.1)
- Updated analysis set (Sec. 6)
- Added Sjogren patient population summary (Sec. 7 and 8)
- Added medical history summary for period 2 (Sec. 7.5)
- Added CFS shift table (Sec. 8.2)
- Added CFS complete resolution summary (CFS=0 at post BL) (Sec. 8.2)
- Added MMRM to estimate treatment difference for secondary endpoints (Sec. 8.2) and updated related section (Sec. 5.1 and 5.4)
- Clarified the duration of detail for ocular surface complication (Sec. 9.1)
- Added SAS sample code (Sec. 12)

2. STUDY OBJECTIVES AND ENDPOINTS

2.1. Objectives

The primary objectives of this study are:

- To evaluate the long-term efficacy of a continuous treatment of IKERVIS® (1mg/mL ciclosporin) eye drops in adult dry eye disease (DED) subjects with severe keratitis on corneal sign and DED symptoms, and to estimate the lag time (if any) to improvement in symptoms (if any).
- To assess the ocular surface complications (defined as corneal ulceration, corneal perforation, loss of visual acuity, and ocular infection) over the three-year study period.

The secondary objectives of this study are:

- To evaluate the efficacy parameters (signs and symptoms), the ocular surface complications, and the quality of life over treatment Periods 1 and 2.
- For 12-month markedly improved subjects, to evaluate and compare signs and symptoms evolution in IKERVIS® group versus Vehicle group during the randomised period of the study (Period 2).
- To evaluate the safety and tolerability of IKERVIS® (1mg/mL ciclosporin) eye drops treatment over the three-year study period.

2.2. Endpoints

2.2.1. Primary Efficacy and Safety Endpoints

- The correlation between change from baseline in CFS score and SANDE symptoms score at each visit, and cross correlation of sign at visit X versus symptoms at visit X+i (i starting from 0), if any.
- Incident rate of ocular surface complications (defined as corneal ulceration, corneal perforation, loss of visual acuity and ocular infection
- Time to onset of ocular surface complications

2.2.2. Secondary Endpoints

Efficacy:

A) In Period 1:

- CFS score and change from baseline at each visit
- Conjunctival fluorescein staining score and change from baseline at each visit
- SANDE symptoms score and change from baseline at each visit
- Symptoms score (5-point scale) and change from baseline at each visit, for each of the five symptoms assessed
- Occurrence and time to become markedly improved (defined as CFS score improvement of 2 or more on the modified Oxford scale during Period 1)

- TBUT and change from baseline at each visit
- Schirmer test and change from baseline at Month 12 visit
- Use of Artificial Tears over the last week and change from baseline at each visit

B) In Period 2:

- CFS score and change from Month 12 visit at each visit
- Conjunctival fluorescein staining score and change from Month 12 at each visit
- SANDE symptoms score and change from Month 12 visit at each visit
- Symptoms score (5-point scale) and change from Month 12 visit at each visit, for each of the five symptoms assessed
- TBUT and change from Month 12 visit at each visit
- Schirmer test and change from Month 12 visit at Month 24 and Month 36 visits
- Use of Artificial Tears (over the last week and change from Month 12 visit at each visit
- Occurrence and time to relapse (increase of CFS score of 2 or more on the modified Oxford scale)

C) In entire study:

- CFS score and change from baseline at each visit
- Conjunctival fluorescein staining score and change from baseline at each visit
- SANDE symptoms score and change from baseline at each visit
- Symptoms score (5-point scale) and change from baseline at each visit, for each of the five symptoms assessed
- TBUT and change from baseline at each visit
- Schirmer test and change from baseline at each visit
- Use of Artificial Tears over the last week and change from baseline at each visit

Quality of Life:

In the randomised markedly improved subpopulation,

• Dry Eye related Quality of life Score (DEQS) summary scores, and change from baseline at Month 6, Month 9, and Month 12 will be presented for Period 1. Change from Month 12 will also be summarized for scores collected in Period 2

Safety and Tolerability:

In the Safety population, safety and tolerability endpoints are:

[figure not shown]
- Intraocular pressure (IOP) and change from baseline at Month 12, Month 24 and Month 36 visits
- Best Corrected Distance Visual Acuity (BCDVA) and change from baseline at Month 6, Month 12, Month 24 and Month 36 visits
- Incidence and severity of ocular and systemic adverse events (AEs) over the three-year study period.

3. STUDY DESIGN

3.1. General Study Design

This is a phase IIIb, prospective, interventional, multicentre, three-year study to explore the long-term evolution of sign and symptoms, and occurrence of complications in dry eye disease subjects with severe keratitis receiving IKERVIS® (1mg/ml ciclosporin) eye drops. All enrolled subjects will enter a period of 12 months of treatment (Period 1) with open-label IKERVIS® treatment [once daily (QD) into the affected eye(s) at bedtime]. At Month 12 visit, markedly improved subjects will continue the study for an additional 24 months randomized, double-masked treatment period (Period 2) to receive either IKERVIS® QD or vehicle QD (at a ratio of 3:2), Figure 1.

Figure 1. Study Design Diagram

IKERVIS will be used with AT (same AT for all patients) up to 6 times per day

Markedly improved subjects are defined as subjects having a corneal fluorescein staining (CFS) score improvement from baseline of 2 grades or more on the modified Oxford scale [unless if the subject had a CFS score of 5 at baseline, the improvement in CFS has to be 3 grades or more] in the study eye. Subjects who are not markedly improved at Month 12 based on the above definition will be terminated from the study.

This study will be conducted in about 36 sites located in European and non-European countries.

3.2. Randomization and Masking

Period 1 of the study is open-label, single arm treatment with IKERVIS®. No randomization is needed in Period 1 (from Baseline for the first 12 months of treatment).

At the beginning of Period 2, (ie. the Month 12 visit), subjects who achieve a marked improvement (ie. CFS score improvement from baseline of 2 grades or more [unless if the subject had a CFS

score of 5 at baseline, the improvement in CFS has to be 3 grades or more]) will be randomly assigned (by the IWRS/IVRS) in a 3:2 ratio to receive either IKERVIS® or Vehicle for two years in a double-masked fashion. The randomization will be stratified by region (Europe vs. non-Europe), and the permuted block randomization will be used within each stratum.

The randomization schedule will be generated and implemented using central randomization via Interactive Response Technology (Rave RTSM). Each randomized subject will receive numbered study medication kits as assigned by Rave RTSM.

Treatment assignments during the Double-Masked Treatment Period will be masked to Santen employees (except Drug Supply personnel), study subjects, and Investigators. The investigator should try to avoid breaking the masking codes. However, in case of emergency only, (i.e. serious adverse event [SAE] and only when this information influences the subject's management), the investigator is entitled to unmask the subject by using IWRS, in order to obtain the study medication information (i.e. IKERVIS® or vehicle) to immediately start the appropriate treatment [to be recorded in the source data and eCRF (electronic Case Report Form)]. A record will be made of the date, time and reason for breaking the code. The investigator should inform the Sponsor immediately after unmasking. The details of this unmasking procedure will be described in a separate document. Subjects unmasked for the management of a SAE will be discontinued from the study.

3.3. Sample Size Determination

The sample size of this study is not planned from a formal sample size calculation since formal statistical hypothesis testing will not be performed for the primary endpoints. In this study, we plan to enroll 350 subjects. Of the 350 subjects, it is estimated that approximately 70% (245 subjects) would become markedly improved in CFS after Month 12 and enter the Period 2 (double-masked randomized period), based on Santen previous IKERVIS studies. With a 3:2 randomization allocation ratio, a sample size of 147 for IKERVIS® and 98 for Vehicle will allow us to detect a difference of 0.4 or more in CFS score with 80% power assuming the standard deviation of the difference is 1.10.

Petroutsos *et al.* (1992) showed that after 6 years of follow-up on DED subjects, a lower-bound of the estimated complication rate was 4% in severe DED subjects. In the current study, 350 subjects treated with IKERVIS® for at least one year would have 95% power to detect at least one ocular complication that occurs at 1% rate with type I error rate of 0.05.

3.4. Visits and Assessments

There are 5 scheduled visits for each subject in Period 1 (open-label treatment period, Day 1 Visit to Month 12 Visit) and 8 additional visits for markedly improved subjects who enter Period 2 (double-masked treatment period, Month 12 Visit to Month 36 Visit). Assessments at each visit and the visit window for each post-baseline assessment are specified in the Assessment Schedule shown on Table 1.

 Table 1.
 Study Design and Schedule of Assessments

	Baseline	Perio	od 1	Perio	od 2	End of Study Visit	
	Day 1	Month ^a 3 (D90), 6 (D180) and 9 (D270) (± 7 days)	Month ^{ah} 12 (D360) (± 7 days)	Month a 15 (D450), 21 (D630), 27 (810) and 33 (D990) (± 7 days)	Month ^a 18 (D540), 24 (D720) and 30 (D900) (± 7 days)	Month ^a 36 (D1080) (± 7 days)/ Early Termination	Unscheduled visit
Informed consent	X						
Demographic information	X						
Inclusion/Exclusion Criteria	X						
Ocular and systemic medical history	X						
Previous and concomitant ocular and systemic medications	X	X	X	X	X	X	X
Artificial tears use b	X	X	X	X	X	X	X
Symptoms evaluation (SANDE) ^c	X	X	X	X	X	X	X
Symptoms evaluation (0-4 point scale) ^c	X	X	X	X	X	X	X
Quality of life questionnaire (DEQS)	X	X ^d	X		X	X	
Best corrected distance visual acuity (BCDVA)	X	X ^d	X		X	X	
Slit lamp examination	X	X ^d	X		X	X	
Tear break up time (TBUT)	X	X	X	X	X	X	X
Corneal and Conjunctival Fluorescein staining (Modified Oxford Scale)	X	X	X	X	X	X	X
Schirmer test (without anesthesia)	X		X		Xe	X	
Intraocular Pressure (IOP)	X		X		Xe	X	X
Urine pregnancy test (women of childbearing potential only)	X	X	X	X	X	X	
Adverse events (AEs)		X	X	X	X	X	X ^f

	Baseline	Perio	od 1	Perio	od 2	End of Study Visit	
	Day 1	Month ^a 3 (D90), 6 (D180) and 9 (D270) (± 7 days)	Month ^{ah} 12 (D360) (± 7 days)	Month a 15 (D450), 21 (D630), 27 (810) and 33 (D990) (± 7 days)	Month ^a 18 (D540), 24 (D720) and 30 (D900) (± 7 days)	Month ^a 36 (D1080) (± 7 days)/ Early Termination	Unscheduled visit
Registration of subjects status in IWRS/IVRS (e.g. enrolment, randomisation, EoS/ET)	X		X			X	X
Compliance with study medication regimen		X	X	X	X	X	X
Dispensation of unpreserved artificial tears	X	X	X	X	X		Хg
Dispensation of open-label study medication	X	X					X g
Dispensation of masked study medication			X^{hi}	Xi	Xi		X g
Collection of used study medication	X	X	X	X	X	X	X

^a Months of 30 days.

^b Artificial tears (AT) use assessed by questioning the subject at each study visit.

^c Symptom of dry eye will be evaluated at each study visit by completing SANDE questionnaire and 5 symptoms using a 0-4 point scale.

^d QoL and BCDVA will NOT be assessed and slit lamp examination will not be performed at Month 3 and 9. TBUT and corneal and conjunctival fluorescein staining which will be performed at each visit.

^e Schirmer test and IOP will NOT be performed at Month 18 and 30 visits.

f Record AEs if the unscheduled visit is after the first study drug administration.

g Dispensation of study medication and/or unpreserved artificial tears if necessary.

h Randomisation of markedly improved subjects at Month 12 visit.

¹ Dispensation of masked study medication (IKERVIS® or Vehicle).

4. **DEFINITIONS**

4.1. Time-Related Terms

4.1.1. Baseline Visit

For this study, the *baseline visit* is the Day 1 Visit when a subject was enrolled into this study (as a non-screen failure subject who signed informed consent) and received open-label IKERVIS treatment in Period 1.

4.1.2. Treatment Start Date and End Date

The treatment start and end dates for each treatment period and the study are defined as follows:

Treatment Period	Treatment Start Date	Treatment End Date
Open-Label Treatment Period (Period 1)	The date of the first dose of the open-label IKERVIS treatment (or Day 1 date)	 The date of the last dose of the open-label IKERVIS treatment The date of the day before the Month 12 Visit will be considered the Period 1 treatment end date for subjects who completed Period 1 treatment. The date of the day before the Exit Visit will be used for subjects who prematurely discontinued from the study. If the Exit Visit date of a non-completer is not available, then the day before the last available visit date will be considered the treatment end date.
Double-Masked Treatment Period (Period 2)	The date of the first dose of the double-masked study treatment (or Month 12 Visit date)	 The date of the last dose of the double-masked study treatment The date of the day before the Month 36 Visit will be considered the Period 2 treatment end date for subjects who completed the study. The date of the day before the Exit Visit will be used for subjects who prematurely discontinued from the study. If the Exit Visit date of a non-completer is not available, then the day before the last available visit date will be considered the treatment end date.

For each treatment period, the treatment end date will be set to missing if the treatment start date is missing.

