7.6. Treatment Compliance

Compliance to the study medication use is tracked on the Compliance eCRF as the number of single dose medication containers not used and returned.

Due to the irregularities in returning containers caused by COVID-19 situation, the treatment compliance will be assessed by study period rather than by intervals based on scheduled visits as specified in the protocol. Since some visits, for example, happened remotely, dispensing or returning of study drug could not happen on a scheduled time. Compliance rate will be calculated for Period 1, and Period 2, respectively.

For a given analysis period, compliance rate will be calculated using the following formula, which assumes that the unreturned containers are not used:

Treatment Compliance Rate (%) in Period x

 $= \frac{\text{No. of dispensed containers-(No. of returned unused containers + No. of unreturned containers)}}{\text{Duration of Period x}} \times 100$

where the Duration of Period x is the number of days subjects should have administered study medication in the analysis period, calculated as

Duration of Period x =end date of study drug in Period x -start date of study drug in Period x.

Compliance rate of \geq 80% will be treated as compliant. Compliance will be summarized continuously and categorically (compliant and non-compliant) for FAS subjects for Period 1 and Period 2 separately. Period 2 summaries will be performed by planned treatment and overall.

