7.7. Exposure to Study Medication

The *extent of exposure* to study medication will be assessed by duration of treatment exposure, derived as:

Duration of treatment exposure = Treatment end date - Treatment start date + 1 Specially,

Period	Treatment Start Date	Treatment End Date
Period 1	Period 1 treatment start date	Period 1 treatment end date
Period 2	Period 2 treatment start date	Period 2 treatment end date
Entire Study Period (for subjects who entered Period 2 and received IKERVIS treatment only)	Period 1 treatment start date	Period 2 treatment end date

For subjects in the Safety Population, the duration of exposure will be summarized using descriptive statistics continuously and categorically for Period 1, Period 2 (by actual treatment received and overall), and for the entire study (for subjects who entered Period 2 and received treatment (IKERVIS/IKERVIS or IKERVIS/Vehicle) or for subjects who received IKERVIS treatment during Period 1 or 2) separately.

The duration of exposure categories are:

- Period 1: 1-90, 91-180, 181-270, or \geq 271 days
- Period 2: 1-90, 91-180, 181-270, 271-360, 361-450, 451-540, 541-630, \geq 631days
- Entire study period: 1-90, 91-180, 181-270, 271-360, 361-450, 451-540, 541-630, 631-720, 721-810, 811-900, 901-990, or \geq 991 days

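### SAP 4.1.2 assigns visit-based treatment end dates without saying when the last-dose date governs, and the 7.6 compliance denominator is one day short

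*SAP*

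**What the plan says.** The Treatment End Date cell of SAP 4.1.2 opens, for Period 1, with "The date of the last dose of the open-label IKERVIS treatment"; Period 2 has parallel wording. The same cell then gives completers the day before the Month 12 or Month 36 visit. For those who left early it states "The date of the day before the Exit Visit will be used for subjects who prematurely discontinued from the study". For those without an exit visit it continues: "If the Exit Visit date of a non-completer is not available, then the day before the last available visit date will be considered" the end date.

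The end date feeds exposure in 4.1.5 and in 7.7, where the formula is "Duration of treatment exposure = Treatment end date - Treatment start date + 1".

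For compliance, SAP 7.6 describes its denominator as "the number of days subjects should have administered study medication in the analysis period" but computes it as "Duration of Period x =end date of study drug in Period x -start date of study drug in Period x", without the +1. The numerator is a container count "which assumes that the unreturned containers are not used". A rate of 80% or more counts as compliant.

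**The concern.** The three visit-based rules between them cover completers, early leavers with an exit visit and early leavers without one. Taken as written, nobody is left for whom the recorded last dose decides the end date. Two programmers could reasonably derive different dates from the same cell.

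The difference matters when drug and study are stopped at different times, and the documents allow for that. SAP 9.2 lists adverse events leading to study drug discontinuation. Protocol 12.2.4.1 records the action taken with the drug separately from whether the event led the patient to leave the study. Protocol 7.5 asks for the early termination procedures but sets no maximum delay after the last dose, and scheduled visits are about 90 days apart.

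At stake are the accuracy of the exposure table, the compliant/non-compliant split, and which medicines count as concomitant. SAP 4.5.1 defines a concomitant medicine by overlap with the study-drug treatment period. If that period ends at the 4.1.2 date, a medicine started after the last drop but before the exit visit could be tabulated as concomitant.

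**Working it through.** The plan states no exposure or compliance result to reproduce, so the check applies its formulas directly.

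**Inputs and assumptions.** Drug starts on Day 1. One container is used per day up to the last dose on Day L, and all unused containers are returned. There are g off-drug days, so the exit visit falls on Day L + g + 1 and the 4.1.2 end date is Day L + g. The 7.6 denominator is assumed to use that date; the SAP does not say so.

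**Formulas.**
- Exposure (7.7): (L + g) − 1 + 1 = L + g. True exposure is L, so the excess is exactly g days.
- Compliance (7.6): 100 × L / (L + g − 1).

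**Main example.** With L = 60 and an exit visit on Day 90, g = 29 and the end date is Day 89. Exposure is 89 − 1 + 1 = 89 days against 60 (89/60 = 1.48, or +48%). Compliance is 60/(89 − 1) = 60/88 = 68.2%.

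| Last dose L | Gap g | SAP exposure (days) | Excess | 7.6 compliance | Against 80% |
|---|---|---|---|---|---|
| 30 | 14 | 44 | +47% | 69.8% | below |
| 60 | 29 | 89 | +48% | 68.2% | below |
| 90 | 14 | 104 | +16% | 87.4% | above |
| 90 | 30 | 120 | +33% | 75.6% | below |
| 180 | 30 | 210 | +17% | 86.1% | above |
| 180 | 60 | 240 | +33% | 75.3% | below |
| 270 | 60 | 330 | +22% | 82.1% | above |
| 270 | 90 | 360 | +33% | 75.2% | below |

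**When the 80% line is crossed.** L / (L + g − 1) < 0.80 requires g > 0.25 L + 1. The smallest such gap is 9 days for L = 30, 17 for L = 60, 24 for L = 90, 47 for L = 180 and 69 for L = 270.

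**Opposite direction.** With no exit visit, a last visit on Day 90 and drug taken to Day 120, the end date is Day 89. Exposure is then 89 days against 120, an understatement of 31 days.

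**The missing +1.** A Period 1 completer seen on Day 360 has end date Day 359. Dosing every day from Day 1 to Day 359 uses 359 containers, but the 7.6 duration is 359 − 1 = 358, so compliance is 359/358 = 100.3%. This error does not depend on how 4.1.2 is read.

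**After correction.** Using the last-dose date and the +1, the main example gives 60 days of exposure and 60/60 = 100% compliance.

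**The case against.** The strongest defence is that the cell names the last dose first, so the visit dates can be taken as stand-ins for when it is unknown. With bedtime dosing, the day before the visit is also the natural last dosing day for anyone still on treatment, and then the rule gives no error. Both points are fair. But the visit rules carry no such condition. The only condition in the cell concerns a missing exit visit date, which shows that the authors wrote one where they wanted one. What remains is an unstated order of precedence.

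It can also be argued that off-drug days while still in the study are properly missed days under the description in 7.6. That is a defensible definition. However, the formula refers to the end date of study drug, and 7.6 neither cites 4.1.2 nor says which meaning applies.

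A reader might infer more than the documents support:

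- **Biased safety rates.** SAP 9.1 reports complications as n and %, odds ratios, a binomial comparison with 4%, and time to first onset. SAP 9.2 counts subjects, and treatment-emergent status in 4.4.1 uses only the start date. No planned rate is specified per unit of exposure.
- **Bias between arms.** The 29.2% against 8.9% instillation site pain in Protocol 4.1.1 comes from another trial. These are rates of pain, not of stopping early, and Period 2 randomises only patients who have already had 12 months of IKERVIS.
- **All early stoppers look non-compliant.** They do so only past the gap shown above. The per-protocol set in SAP 6 is not tied to the 80% rule.
- **A gap between periods in 4.1.5.** Period 1 ends the day before Month 12, and Period 2 can start on the Month 12 date, so the two are contiguous unless the first masked dose is recorded later.
- **A zero compliance denominator.** This arises only if the end date equals the start date, for example with an exit visit on Day 2. The +1 removes it.

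**Conclusion.** The point holds as a minor one about rules that, followed literally, give wrong numbers. Exposure is overstated by exactly the off-drug gap in subjects who stopped before the exit visit. It is correct for those dosed up to the day before the visit, and it can be understated when there is no exit visit. Compliance is lowered if 7.6 uses the 4.1.2 date, and a fully adherent subject is reclassified only when the gap exceeds about a quarter of the time on drug. The missing +1 is certain but small: 100.3% for a fully adherent Period 1 completer.

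The exposure error rests on the literal reading of 4.1.2; if the visit dates are only a fallback, it disappears wherever the last dose is known. The number of subjects affected cannot be derived from the documents. The effect stays within the descriptive exposure and compliance summaries and the concomitant-medication overlap.

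**What to change.** - In SAP 4.1.2, state that the recorded last-dose date governs where available. Keep the visit-minus-one-day dates as a fallback, and flag every date set that way.
- In SAP 7.6, state that the duration uses this same end date, and add 1 to it so that it matches 4.1.5, 7.7 and its own description.
- Confirm that the eCRF captures a last-dose date. SAP 7.6 mentions only container counts, and the action-taken item in Protocol 12.2.4.1 is not listed with a stop date.

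The cost is SAP wording and programming, plus an eCRF field if none exists. Stated exposure will become slightly smaller. Without a collected last-dose date the visit-based proxy stays in use, and the gain is limited to the +1, the explicit rule and the flag on imputed dates.
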